2.3.5 HANDLING OF MISSING, INCOMPLETE, AND REPEAT DATA

The handling of missing data and/or missing planned visits is described in the following section for the primary endpoint and secondary endpoints.

Percentage change in ulcer Area – Primary Endpoint:

The percentage change in target ulcer area over the 12-week treatment period is derived using the baseline area and the area recorded at Study Visit 13. Missing values and/or visits may occur at these visits if data is not collected or a subject discontinues from the treatment due to wound closure or early termination. In cases where the target ulcer area is missing or an ARANZ image cannot be taken due to the ulcer being closed in the opinion of the Investigator, the ulcer area at the Study Visit will be imputed as 0 cm².

In circumstances where the ulcer area is missing at the Study Visit 13 for subjects that have not withdrawn prematurely due to closure, the last observation carried forward (LOCF) method will be used.

Percentage change in ulcer Depth/Volume – Key Secondary Endpoint:

The methods detailed above for the handling of missing/incomplete data regarding the primary endpoint will also be used for Depth and Volume.

Proportion of subjects with confirmed ulcer closure – Secondary Endpoint:

The subject's ulcer closure status (open or closed) will be assessed by the Investigator at each study visit. Closure is confirmed at one-week post initial ulcer closure. Missing values and/or visits may occur at these visits if data is not collected at the Study Visit, or a subject discontinues from the treatment due to wound closure or early termination. Missing data may also exist if the one-week closure

Document Number: 1004313
Document Version: 06

Document Part: 000
Document Status: Released

ST:

9 7 5

Reference:

CE/052/PIC

Customer Code:

0 5

confirmation visit is not attended. In cases where the ulcer closure status is missing at a Study Visit or the subject is withdrawn from the study, the Last Observation Carried Forward (LOCF) method will be used (with the exception of the confirmatory period).

In addition, two separate sensitivity derivations will be performed to account for missing data:

- Worst case: In cases where subjects had missing data over the confirmatory target ulcer closure period (1 week follow-up) and it is unknown whether the closure is confirmed, these will be imputed as: Confirmed Closure=No.

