- Best case: In cases where subjects withdraw from the study prior to the end of the 12-week treatment period (except in cases where the ulcer has closed), the following will be imputed: Confirmed Closure=Yes.

Time to achieve complete closure – Secondary Endpoint:

Once a subject achieves complete ulcer closure as defined above, the time to complete ulcer closure will be calculated as the time interval in number of days between the date of randomization (i.e. Study Visit 1) and the date of the initial observation of the wound ulcer closure. For those subjects who drop out or who do not achieve the complete wound closure during the 12-week treatment period, the time to complete wound closure will be considered being censored at the last visit date (censored date) of the treatment period (i.e. from Study Visits 2 to 13) or 84 days (i.e., 7 days x 12 weeks), whichever occurs earlier. There is no missing data for time to achieve complete closure.

Difference between treatments in Health Related Quality of Life (HRQoL) – Secondary Endpoint:

The EQ-5D and CWIS instruments will be completed at Randomisation (Study Visit 1) and End of treatment. Missing data can occur with the questionnaires due to missed questions or the subject being unwilling to answer. Missed visits may also cause missing data. In cases where questions are skipped, the missing responses will be coded as per the instrument guidelines. Separately, in cases where there are missing individual responses (not complete missing questionnaires) contained on the end of treatment questionnaire, these will be coded as the Last Observation Carried Forward (LOCF) from the baseline questionnaire.

Document Number: 1004313
Document Version: 06

Document Part: 000
Document Status: Released

Ulcer progression parameters – Exploratory Endpoint:

Assessment of change in target ulcer progression parameters over the 12-weeks and comparison between treatments including: Estimation of the types of tissue present on the target ulcer, Presence of Infection/Clinical signs of infection, Condition of peri-wound skin, Need for administration of antibiotics and additional interventions, dressing wear time, pain on removal of dressing and at initiation of, and during, therapy. Missing values and/or visits may occur at these visits if data is not collected or a subject discontinues from the treatment due to ulcer closure or early termination.

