- Ulcer Closed/Ready for surgical closure =Yes at last attended Study Visit i, Ulcer Closed=missing at Follow up assessment (Visit 14). Confirmed Closure = missing
- Ulcer Closed/Ready for surgical closure =No at last attended Study Visit i. Confirmed Closure = No

In cases where the ulcer closure status is missing at a Study Visit, the Last Observation Carried Forward (LOCF) method will be used.

21. The derivation for whether confirmed ulcer closure was achieved will be repeated to form two further separate variables, with the exceptions below:

- i. In cases where subjects had missing data over the confirmatory target ulcer closure period (1 week follow-up) and it is unknown whether the closure is confirmed, these will be imputed as: Confirmed Closure=No. All remaining scenarios will be derived as described in the previous derived variable.
- ii. In cases where subjects withdraw from the study prior to the end of the 12-week treatment period (except in cases where the ulcer has closed), the following will be imputed: Confirmed Closure=Yes. All remaining scenarios will be derived as described in the previous derived variable.

22. The components of the CWIS will be derived as follows at baseline and end of treatment.

a) Physical symptoms and daily living

Each individual response will be coded by the following formulae:

Document Number:	1004313	Document Part:	000
Document Version:	06	Document Status:	Released

ST:

9

7

5

Reference:

CE/052/PIC

Customer Code:

0

5

Not at all/Not applicable – 5

Seldom/Slightly – 4

Sometimes/Moderately – 3

Frequently/Quite a bit – 2

Always/Very – 1

An overall score for this domain will then be calculated as the sum of the 24 individual values (12 individual values each for experience and stress related measures).

The overall score will then be transformed onto a scale of 0-100 using the following formula:

$$[(\text{Overall actual score (sum of 24 individual scores)} - \text{minimum possible score}) / \text{range of possible scores}] * 100$$

If all 24 questions are completed, the minimum value =24 and the range of scores = (120 - 24) = 96

b) Social Life

Each individual response will be coded by the following formulae:

Not at all/Not applicable – 5

Seldom/Slightly – 4

Sometimes/Moderately – 3

Frequently/Quite a bit – 2

Always/Very – 1

An overall score for this domain will then be calculated as the sum of the 14 individual values (7 individual values each for experience and stress related measures).

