4.10 Secondary Variables

Percentage change in target ulcer depth and volume over the 12-week treatment period (Key Secondary)

The primary analysis and accompanying summaries relating to change in target ulcer area will be repeated separately for both the change in target ulcer depth and volume over the 12-week treatment period with a single exception. The initial models will include baseline ulcer depth and volume respectively for the two key secondary objectives rather than baseline ulcer area as detailed in the primary analysis.

The baseline depth, final depth, absolute change in depth and percentage change in ulcer depth over the 12-week treatment period will be summarized separated by treatment, centre, wound type and baseline depth (<median/>=median). Further summaries will be produced separated by the covariates used in the final model. The ulcer depth, change in depth and percentage change in depth will be summarized by Study Visit (2-12) and treatment, centre, wound type and baseline depth (<median/>=median). Summaries will utilize the Per Protocol Population and will be repeated for the Full Analysis Set. The summaries detailed for ulcer depth will be repeated for the target ulcer volume.

Proportion of subjects achieving confirmed target ulcer closure over the 12-week treatment period

The proportion of subjects achieving confirmed target ulcer closure, either by surgical intervention or secondary intention, over the 12-week treatment period will be analyzed as follows using the Full Analysis Set. An initial logistic regression model will contain covariates for treatment, center, wound type, baseline (defined as Study Visit 1) ulcer area and duration of ulcer. Pooling of centers with less than 10 subjects will be performed as described in the primary analysis. A forward selection procedure will be used for the addition of other baseline covariates with an F-value to attain a significance level of 0.1. Further baseline covariates to be assessed as

part of this procedure include: subject age, body mass index, baseline ulcer depth and baseline level of exudate.

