The resulting analysis presented will correspond to the final model from the forward selection procedure. The results for the initial model will also be presented. For each of the effects in the initial and final model, the p-value, odds-ratio and corresponding 95% confidence interval will be presented. Secondary subgroup analyses may be conducted as a result of the covariate analyses. Additionally, treatment will be fitted on its own in a further logistic regression model. In each case, the residuals will be examined for outliers using influence plots of diagnostic statistics (Hat Matrix Diagonal, Pearson residuals, Deviance residuals, DFBETAs, C and CBAR, DIFDEV and DIFCHISQ). For each model, overdispersion will be tested for by examining the deviance and pearson statistic divided by their degrees of freedom. If these are not approximately equal to 1 then an adjusted analysis may be used for overdispersion using quasi-likelihood methods.

Cross-tabulations of each of the covariates (continuous covariates will be categorized for purposes of the cross-tabulations) with treatment and closure, will be generated for each of the baseline covariates included in the final model.

The 95% confidence interval (unadjusted for all covariates) for the difference between treatments in terms of the percentage healed by 12 weeks will be generated along with the Chi-square test p-value using the Per Protocol Population.

Two separate sensitivity analyses will be performed to ensure that the efficacy findings are not reliant on assumptions made in either the analysis or derivations; the analysis for the proportion of subjects achieving confirmed ulcer closure will be repeated with the following modifications using the Full Analysis Set only:

- 1) Worst case: In cases where subjects had missing data over the confirmatory target ulcer closure period (1 week follow-up) and it is unknown whether the closure is confirmed, these will be imputed as: Confirmed Closure=No.
- 2) Best Case: In cases where subjects withdraw from the study prior to the end of the 12-week treatment period (except in cases where the ulcer has closed), the following will be imputed: Confirmed Closure=Yes.

Whether confirmed closure was achieved will be summarised by Study Visit (Note: initial observation of closure will be summarized not the visit where closure was confirmed). The wound status (open/closed/re-opened) will be summarized for the Study Visit 14 assessment.

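### The closure best case leaves subjects last seen closed but without a confirmation visit as missing, so no confirmed-closure analysis ever counts them as closed

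*SAP*

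**What the plan says.** SAP 4.3 item 20 derives confirmed closure from the last attended study visit and Visit 14. An ulcer still open at the last attended visit scores No. An ulcer recorded as closed or ready for surgical closure scores Yes or No according to Visit 14. If Visit 14 is missing, the rule is "Ulcer Closed=missing at Follow up assessment (Visit 14). Confirmed Closure = missing". Protocol 9.4 has the same rule, without the ready-for-surgery wording.

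SAP 2.3.5 fills other gaps in closure status by LOCF but not this one: "method will be used (with the exception of the confirmatory period". The LOCF sentences after item 20 and in Protocol 9.4 carry no such exception.

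The main model is a logistic regression of confirmed closure, which "over the 12-week treatment period will be analyzed as follows using the Full Analysis Set" (SAP 4.10). Two sensitivity analyses follow:

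- **Worst case.** Where the confirmation week is missing and "it is unknown whether the closure is confirmed, these will be imputed as: Confirmed Closure=No" (SAP 4.3 item 21i).
- **Best case.** It applies to early withdrawals, "except in cases where the ulcer has closed), the following will be imputed: Confirmed Closure=Yes" (SAP 2.3.5; also 4.3 item 21ii and 4.10). All other situations follow item 20.

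Both are repeated for time to closure with the censoring flag changed and the times left as they are. On that endpoint SAP 2.3.5 states: "There is no missing data for time to achieve complete closure".

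**The concern.** A best case should give the unknown outcomes their most favorable value. This one gives Yes to subjects who left with an open ulcer and gives no value to subjects whose last record was a closed ulcer. The second group is the more likely of the two to have healed.

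Closers stop study treatment and return for one further visit, so a single missed appointment is enough to make the outcome missing. The study is open-label (Protocol 8.2), so attendance after closure could differ by arm. If it does, the confirmed-closure comparison shifts, and no planned confirmed-closure analysis shows how far it would shift if these closures were real. Two secondary endpoints are exposed: the proportion closed and the time to closure.

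**Working it through.** The documents state no closure rate, no re-opening rate and no rate of missed confirmation visits, so there is no plan figure to reproduce. The rules are traced first, then illustrated on assumed counts.

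**Step 1: how each group is scored.**

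| Group | Main | Worst case | Best case |
|---|---|---|---|
| Seen closed, Visit 14 attended | As observed | As observed | As observed |
| Last seen closed, Visit 14 missed | Missing | No | Missing |
| Ready for surgery, not yet seen closed, Visit 14 missed | Missing | No | Missing, or Yes if treated as an open withdrawal; the SAP does not say |
| Withdrawn early, last seen open | No | No | Yes |

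That a missing response leaves the logistic model is an inference: the SAP describes no other handling for it. No cell in the second row is Yes.

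**Step 2: time to closure.** Item 19 gives subjects who close without confirmation a time, the date closure was first recorded. SAP 2.3.2, SAP 2.3.5 and Protocol 9.4 censor subjects without confirmed closure. Read together, these subjects stay in the model as censored, although item 19 does not state the flag. The repeated worst case then changes nothing for them, and the repeated best case also leaves them without an event.

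**Step 3: estimators for one arm.** Let N = subjects, C = confirmed closed, m = seen closed without Visit 14, w = withdrawn open, and q = share of m that would have been confirmed. Assume withdrawn open ulcers stay open.

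- Main = C/(N - m)
- Worst case = C/N
- Best case as planned = (C + w)/(N - m)
- Best case with seen-closed scored Yes = (C + w + m)/N
- Truth = (C + q·m)/N

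The truth is a weighted average of the main estimate and q. So the main estimate is too low only if q exceeds the observed closure rate.

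**Step 4: assumed example.** N = 80 and 32 ulcers seen closed per arm; 10% re-open (q = 0.9); confirmation missed by 15% of closers in arm A and 5% in arm B; w = 12 per arm. Then m = 4.8 and 1.6. C = 32 × 0.85 × 0.9 = 24.48 and 32 × 0.95 × 0.9 = 27.36.

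| | Arm A | Arm B | A - B (points) |
|---|---|---|---|
| Truth | 28.80/80 = 36.0% | 28.80/80 = 36.0% | 0 |
| Main | 24.48/75.2 = 32.6% | 27.36/78.4 = 34.9% | -2.3 |
| Worst case | 24.48/80 = 30.6% | 27.36/80 = 34.2% | -3.6 |
| Best case as planned | 36.48/75.2 = 48.5% | 39.36/78.4 = 50.2% | -1.7 |
| Best case, seen-closed Yes | 41.28/80 = 51.6% | 40.96/80 = 51.2% | +0.4 |

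All three planned differences lie on one side of the truth; with the changed best case, the two sensitivity analyses span it.

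**Step 5: what the result depends on.**

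- *Split of missed visits.* Exchange the arms and every sign reverses. With 10% missed in both arms, C = 25.92 and m = 3.2. The main estimate is then 25.92/76.8 = 33.8% in each arm against a truth of 36%, and the difference is 0.
- *q.* At q = 0.3 the truth in arm A is (24.48 + 1.44)/80 = 32.4%, so the main 32.6% is slightly too high.
- *Split of withdrawals.* With w = 4 versus 12, the planned best case is 28.48/75.2 - 39.36/78.4 = 37.9% - 50.2% = -12.3 points. With 12 versus 4 it is 48.5% - 31.36/78.4 (40.0%) = +8.5. These swings come from open withdrawals and say nothing about missed confirmation visits.

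**The case against.** A reader might infer that every planned closure estimate understates closure. The documents do not support that. The best case pushes the rate up through open withdrawals: in arm A, three of them are enough to pass the true 36%, (24.48 + 3)/75.2 = 36.5%. The plan allows for 20% drop-out, and 16 of 80 would give 40.48/75.2 = 53.8%. So worst and best case can enclose the closure rate of an arm. What remains is that the upward movement comes from a different group of subjects.

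Nor is it true that no planned analysis treats these subjects as closed. The primary endpoint sets the area of a closed ulcer to 0 cm² without waiting for confirmation (SAP 2.3.1). Unconfirmed closure is summarized by visit (SAP 4.10), and the closure-method table is first run on all closed ulcers (SAP 4.12). The gap is confined to the confirmed-closure models and their sensitivity analyses.

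Three further objections stand. Item 20 also covers ulcers still open and awaiting surgery, so a missing value does not always follow an observed good outcome, and scoring the whole group Yes would be wrong. The statement that time to closure has no missing data is coherent once these subjects are read as censored. And the example's inputs are assumptions: its 2.3 points compare with a standard error of about √(2 × 0.36 × 0.64/80) = 7.6 points, on an endpoint that does not drive the sample size.

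One might also want the main analysis to score these subjects No. That would only duplicate the worst case, and in the example it would move the error from -2.3 to -3.6 points.

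**Conclusion.** The point holds for the best case. By its own rule, it credits withdrawals last seen open and leaves those last seen closed without a value. No confirmed-closure model or sensitivity analysis counts the latter as closed, so the two sensitivity analyses do not bracket the effect of missed confirmation visits.

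The size cannot be fixed from the documents. In the assumed example the error in the treatment difference is 1.7 to 3.6 points across the three planned analyses. It is zero when the arms have equal closure and equal missed visits, and its sign follows the arm with more missed visits. The example assumes that withdrawn open ulcers stay open, that withdrawals are equal by arm, and that 90% of unconfirmed closures would have been confirmed. The primary endpoint is not affected.

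**What to change.** 1. In SAP 4.3 item 21ii, 2.3.5 and 4.10, score subjects seen closed with a missing confirmation visit as Confirmed Closure = Yes in the best case. Protocol 10.3.2 carries the same best-case rule and should match.
2. Show subjects recorded as ready for surgical closure but not yet seen closed as a separate group, and state how the best case scores them.
3. Carry the changed flag into the repeated time-to-closure best case. State in item 19 that these subjects are censored in the main time analysis.
4. Reconcile the LOCF sentences after item 20 and in Protocol 9.4 with the exception in SAP 2.3.5. Read literally, they would carry a closed status into Visit 14, against the rule that makes it missing.
5. Report missed confirmation visits by arm. The best case still moves with the split of open withdrawals, so this count is needed to interpret it.

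The main-analysis rule need not change. The cost is wording in the SAP, matching wording in the protocol, and slightly more analysis work.
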